10.2.3 Collection and Reporting of SAEs

When an SAE occurs through the AE collection period it should be reported according to the following procedure:

A Takeda SAE form must be completed, in English, and signed by the investigator immediately or within 24 hours of first onset or notification of the event. The information should be completed as fully as possible but contain, at a minimum:

A short description of the event and the reason why the event is categorized as serious.

- Subject identification number.
- Investigator's name.

• Relationship to study procedure.

The SAE form should be transmitted within 24 hours to the attention of the contact listed in Section 1.1.

Any SAE spontaneously reported to the investigator following the AE collection period should be reported to the sponsor if considered related to study participation.

Reporting of serious prestudy events will follow the procedure described for SAEs.

10.3 Follow-up of SAEs

If information not available at the time of the first report becomes available at a later date, the investigator should complete a follow-up SAE form (or provide other written documentation and fax it within 24 hours of receipt. Copies of any relevant data from the hospital notes (eg, electrocardiograms, laboratory tests, discharge summary, postmortem results) should be sent to the addressee, if requested.

All SAEs should be followed up until resolution or permanent outcome of the event. The timelines and procedure for follow-up reports are the same as those for the initial report.

10.3.1 Safety Reporting to Investigators, IRBs, and Regulatory Authorities

The sponsor is responsible for submission of AEs and SSRs to regulatory authorities in accordance with local reporting requirements or the sponsor's postmarketing commitments.

The sponsor will be responsible for reporting all suspected unexpected serious adverse reactions (SUSARs) and any other applicable SAEs to regulatory authorities, including the European Medicines Agency, investigators and IRBs or IECs, as applicable. Relative to the first awareness of the event by/or further provision to the sponsor or sponsor's designee, SUSARs will be submitted to the regulatory authorities as expedited report within 7 days for fatal and life-threatening events and 15 days for other serious events, unless otherwise required by national regulations. The sponsor will also prepare an expedited report for other safety issues where these might materially alter the current benefit-risk assessment or consider changes in overall conduct of the trial. The study site also will forward a copy of all expedited reports to his or her IRB or IEC.

11.0 STUDY-SPECIFIC COMMITTEES

Not applicable

12.0 DATA HANDLING AND RECORDKEEPING

The full details of procedures for data handling will be documented in the Data Management Plan or equivalent.

12.1 CRFs (Paper)

Completed CRFs are required for each subject.

The study site will supply CRFs for use during the study. These forms are used to transmit the information collected in the performance of this study to the sponsor and regulatory authorities, as applicable. CRFs must be completed in English. All paper CRFs must be filled out legibly in black or blue ballpoint ink (use of black ink is preferred).

Corrections are to be made by making a single-line strikeout of the incorrect information and writing in the revisions. All corrections must be initialed and dated. Reasons for significant corrections should additionally be included. All new additions are to be made with the date and sign, or sign and seal affixed. Corrections to eCRFs will be made directly in the system, and an audit trail of changes will be maintained at the site.

The principal investigator must review the CRFs for completeness and accuracy and must sign and date the appropriate CRFs as indicated. Furthermore, the investigator must retain full responsibility for the accuracy and authenticity of all data entered on the CRFs.

After submission of the CRFs to the sponsor, any change of, modification of or addition to the data on CRFs should be made by the investigator with use of change and modification records of CRFs (Data Clarification Form). The principal investigator must review the Data Clarification Form for completeness and accuracy, and must sign, or sign and seal, and date the form.

After the lock of the study database, any change of, modification of or addition to the data on the CRFs should be made by the investigator with use of change and modification records of the CRFs.

CRFs may be reviewed for completeness and acceptability at the study site during periodic visits by the sponsor or its designee, as applicable. The sponsor or its designee will be permitted to review the subject's medical and hospital records pertinent to the study to ensure accuracy of the CRFs. The completed CRFs are the sole property of the sponsor and should not be made available in any form to third parties, except for authorized representatives of appropriate governmental health or regulatory authorities, without written permission of the sponsor.

12.2 Record Retention

The investigator agrees to keep the records stipulated in Section 12.1 and those documents that include (but are not limited to) the study-specific documents, the identification log of all participating subjects, medical records, temporary media such as thermal sensitive paper, source worksheets, all original signed and dated informed consent forms, subject authorization forms regarding the use of personal health information (if separate from the informed consent forms), and copies of all paper CRFs and query responses to enable evaluations or audits from regulatory

authorities, the sponsor or its designees. Any source documentation printed on degradable thermal sensitive paper should be photocopied by the site and filed with the original in the subject's chart to ensure long term legibility. Furthermore, International Conference on Harmonisation (ICH) E6 Section 4.9.5 requires the investigator to retain essential documents specified in ICH E6 (Section 8) until at least 2 years after the last approval of a marketing application for a specified drug indication being investigated or, if an application is not approved, until at least 2 years after the investigation is discontinued and regulatory authorities are notified. In addition, ICH E6 Section 4.9.5 states that the study records should be retained until an amount of time specified by applicable regulatory requirements or for a time specified in the study site agreement between the investigator and sponsor.

Refer to the study site agreement for the sponsor's requirements on record retention. The investigator should contact and receive written approval from the sponsor before disposing of any such documents.

13.0 STATISTICAL METHODS

13.1 Statistical and Analytical Plans

A statistical analysis plan will be prepared and finalized prior to database lock. This document will provide further details regarding the definition of analysis variables and analysis methodology to address all study objectives. A data review may be conducted prior to database lock to assess completeness of the study database and appropriateness of the planned statistical methods.

13.1.1 Analysis Sets

The full analysis set (FAS) is defined as all subjects who completed the Study Entrance Visit and received a study wearable technology with at least 1 day of assessments completed. This will be the data set for primary analysis. In this study, 2 kinds of analysis sets are defined: FAS, and safety analysis set. The definition of each analysis set will be described in the Handling Rules for Analysis Data or equivalent.

The safety set will include all subjects who were enrolled and completed the Study Entrance Visit. It is likely that the safety set will be the same as the FAS.

The sponsor will verify the validity of the definitions of the analysis sets as well as the rules for handling data, with consulting a medical expert as needed. If necessary, the Handling Rules for Analysis Data will be supplemented with new handling rules that were not discussed at the planning stage. The Handling Rules or equivalent for Analysis Data must be finalized prior to database lock.

13.1.2 Analysis of Demographics and Other Baseline Characteristics

Summary statistics (mean, SD, median, minimum, and maximum) for age, length of major depressive episode (MDE), number of prior MDEs, scores on PROs (COLOMA), scores on CANTAB cognitive test measures at enrollment will be calculated. Distributions of subjects by sex, and antidepressant class may be summarized if applicable.

Demography tables will be presented for the all enrolled set and the per protocol set. Detailed subject listings will be located in the appendices.

13.1.3 Analysis of Wearable Technology Data Collection Compliance (Coprimary Aim)

This is a coprimary study endpoint, and will be analyzed by assessing the number of wearable cognitive and mood assessments completed for each study day by the subject, as a proportion of the assessments requested. For each subject the percentage of study wearable assessments completed will be calculated and reported in tables overall and as a function of study day.

13.1.4 Analysis of Validity of Wearable and Mood Testing (Coprimary Aim)

This corresponds to the other coprimary aim of the study. Individual subject data on the wearable n-back cognitive test will be analyzed using a longitudinal nonlinear mixed model approach,

which characterizes subject performance as a combination of an intercept and a slope, representing their overall ability and a learning effect, thereby reducing the dimensionality of the cognitive data. These derived cognitive performance parameters from the n-back will be correlated with performance on CANTAB measures of working memory (SWM), attention and concentration (RVP), and executive function (CANTAB SWM Strategy and One Touch Stockings) and using a Pearson correlation coefficient, or nonparametric equivalent, depending on the observed distribution of data. These are the cognitive domains believed to be assessed by the n-back test.

coefficients observed, rather than significance levels. No inferential statistical tests will be carried out, and therefore no adjustment for multiple comparisons is required.

13.1.5 Qualitative Analysis

Qualitative assessment of factors relating to compliance will be obtained from the examination of themes emerging from 3 sources:

- 1. Semistructured study entry interviews (Section 9.1.14.1 Study Day 1) focusing on subject's expectations, motivation, and understanding around cognitive testing and technology.
- 2. Study technical support queries and logs of within-study subject interactions from phone contacts (Section 9.2.4)
- 3. Semistructured end of study interviews (Section 9.1.14.2 Final Visit, Study Day 44) exploring subjects' experience of the application over time, any changes in motivation and compliance, and the contextual factors that might have contributed to those changes.

Interpretative Phenomenological Analysis will be used to analyze the qualitative data. To increase the rigor and validity of the analysis, and as a form of triangulation, the analysis will be conducted by 3 members of the research team (the lead qualitative researcher and 2 others). Analysis will involve 2 stages:

- 1. Data management, which will include:
 - a) Familiarization with the data, reading notes, and/or listening to the audio dialogue in order to extract main themes and ideas.
 - b) Thematic framework development, identifying the key issues and concepts present in the data and creating themes both inductively, based on the data, and deductively, based on the research questions.
- 2. Interpretation stage, which will include focused defining the main concepts and mapping the ways in which different parts of the data are related to each other.

13.1.6 Safety Analysis

AEs will be summarized using the safety set. No statistical testing or inferential statistics will be generated. Data will be summarized using preferred term and primary system organ class.

13.2 Interim Analysis and Criteria for Early Termination

No interim analysis is planned.

13.3 Determination of Sample Size

The proposed sample size of 30 is commensurate with usual practice for feasibility studies [40]. Using a sample size of 30, will be able to estimate a compliance rate of 80% to within a 95% CI of $\pm 12.8\%$. The proposed sample size also provides 80% power to detect correlations of r=0.5, as per the secondary outcomes.

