Using a sample size of 30, will be able to estimate a compliance rate of 80% to within a 95% CI of $\pm 12.8\%$. The proposed sample size also provides 80% power to detect correlations of r=0.5.

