3.1. Descriptive Statistics

Compliance across the study will be transformed into a binary variable for mood and n-back, with days where participants completed testing coded as 1 and days with no data coded as 0. The percentage of days with data will be computed overall and by study week and tabulated.

For each subject, n-back performance across the study will be characterised by four summary variables – the mean, capturing global levels of performance, root mean square of successive differences (RMSSD), capturing variability in performance, and two measures extracted from mixed-effect modelling of the data: intercept and slope, representing initial performance and learning. These summary measures will be tabulated.

Daily mood assessment will be summarised across the study, capturing the overall level of mood across the study whole, and by study week. Means, standard deviation, RMSSD, median, number of subjects and minimum and maximum will be calculated and tabulated.

Activity data from the phone and the watch and heart rate from the watch will be aggregated by day and study week, and means, standard deviation, median, number of subjects and minimum and maximum will be calculated and tabulated.

For each of the CANTAB and PRO outcome variables, mean values, standard deviation, median, number of subjects, and minimum and maximum values will be tabulated by time point.

The output will also contain box plots/ line graphs of mean values (absolute scores) by time point, along with individual subject trajectories for each outcome variable.

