3.2. Primary analysis: Compliance

Compliance with daily mood testing and daily n-back testing will be analysed separately. We will report the overall compliance (% completed testing sessions) over the six weeks of the study. The relationship between overall rates of compliance with baseline subject characteristics (CCI) will be explored through a series of bivariate correlations. These will be Pearson correlations or Spearman's rank correlation coefficient, depending on the observed distribution of the variables. As this is an exploratory study, no adjustment will be made for multiple comparisons.

will be carried out using a series of Chi-square tests.

3.2.1.Logistic Mixed-model (LMM)

We expect compliance with testing to decline over the course of the study, therefore we will use a logistic regression mixed effect model to analyse the effect of time on compliance. Day will be used as fixed factor, and subject as a random effect. We plan on testing the impact of covariates on compliance, including baseline Covariates

Covariates which do not make a significant contribution will not be carried forward. Final model will be selected on the basis of Bayes Information Criterion.

3.2.1.1. Model specification:

<< variable>=subject + day + covariate + covariate * day.

Parameters will initially be analysed without transformation, but if the data suggest otherwise, an appropriate transformation (e.g. logarithmic, square root or reciprocal) will be applied. The analysis will include the calculation of effect sizes. The assumptions of the logistic regression model will be investigated by

examining the distribution of residuals and the pattern of residuals versus fitted values. Where non-normality or non-constant variance is observed, a transformation will be applied so that the assumptions are satisfied.

Transformations will be selected by applying different transformations iteratively (e.g. logarithmic, square root, reciprocal) followed by visual inspection of the cumulative normal plot, histogram of residuals and plot of residuals vs. fitted values. The most suitable transformation in terms of normality and constant variance will be selected. If no suitable transformation can be found, then non-linear models will be considered.

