6.6. Descriptive Statistics

Descriptive statistics for outcome variables (N, Mean, SD, median, minimum, maximum) by time point, including baseline and familiarisation. For daily n-back RMSSD, intercept and slope will also be reported. For daily mood, RMSSD will also be reported.

Table 2.1 Descriptive Statistics – Daily n-back compliance

	Overall	Week1	Week2	Week3	Week4	Week5	Week6
	Overall	Weeki	- VVEEKZ			vveek5	
Mean	94.16	92.63	90.78	93.55	96.31	98.62	93.09
Median	90	89	92	91	96	97	91
SD	5.5	4.3	5.6	4.9	4.2	5.0	4.8
Minimum	80.00	30.00	34.00	33.00	30.00	44.00	23.00

Maximum	100.00	100.00	100.00	100.00	100.00	100.00	100.00	
Overall Rate	92.95	92.63	90.78	91.86	95.43	96.40	90.58	
Table 2.2	le 2.2 Descriptive Statistics - Daily mood compliance							
Table 2.3	Descriptive Statistics - Daily n-back performance							
Table 2.4	Descriptive Statistics - Daily mood assessment						٠	
Table 2.5	Descriptive Statistics – Steps							

Table 2.5 Descriptive Statistics Steps

Table 2.6 Descriptive Statistics – Heart Rate

Table 2.7 Descriptive Statistics – COI

Table 2.8 Descriptive Statistics - CCI

Table 2.9 Descriptive Statistics – CCI

Table 2.10 Descriptive Statistics – CANTAB ERT

Table 2.11 Descriptive Statistics – CANTAB SWM

Table 2.12 Descriptive Statistics – CANTAB RVP

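### The stated precision for compliance does not follow from its own inputs: 80% in 30 subjects gives a 95% CI of about ±14.3 points, not ±12.8

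*Protocol*

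**What the plan says.** Protocol 13.3 (Determination of Sample Size) supports 30 subjects in three ways: usual practice for feasibility studies, a precision statement for compliance, and 80% power for a correlation of 0.5. The precision statement reads "Using a sample size of 30, will be able to estimate a compliance rate of 80% to within a 95% CI of" ±12.8%. The Sample Size Justification in Protocol 2.0 (Study Summary) repeats it with the same rate and half-width. Neither place names a formula or gives an SD.

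The analysis sections treat compliance as follows:

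- Protocol 13.1.3: "For each subject the percentage of study wearable assessments completed will be calculated and reported in tables overall" and by study day.
- SAP 3.1 codes each day as 1 or 0, separately for mood and n-back, and then: "The percentage of days with data will be computed overall and by study week and tabulated".
- SAP 3.2: "Compliance with daily mood testing and daily n-back testing will be analysed separately". Overall compliance there is the percentage of testing sessions completed.
- SAP 6.6: "Descriptive statistics for outcome variables (N, Mean, SD, median, minimum, maximum) by time point".

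None of the visible SAP text on compliance plans a confidence interval for the rate. SAP 3.3 does plan 95% CIs for the correlations.

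**The concern.** The sample size, the rate and the confidence level are all printed, so the half-width can be checked directly, and it does not come out. It is the only numerical statement of precision for the compliance co-primary. The Study Summary says the study is meant to guide later ones and will describe adherence rates without inferential tests, so the precision of that estimate is what the sample size buys. Someone planning a later study from this text cannot tell which rate or which formula was used.

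A second mismatch lies behind the first. A binomial half-width treats each subject as a single yes/no outcome. The planned endpoint is a percentage per subject, and the precision of its mean depends on how much subjects differ. For that endpoint the true precision could be better or worse than the printed figure.

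**Working it through.** **Inputs** (Protocol 13.3, repeated in 2.0): n = 30; rate p = 0.80; 95% confidence, taken as two-sided because of the ± form; stated half-width 12.8 points.

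**Step 1. Try to reproduce the plan's figure.** Wald half-width = z × √(p(1 − p)/n).

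1.96 × √(0.80 × 0.20 / 30) = 1.96 × 0.0730 = 0.1431, that is ±14.3 points (65.7% to 94.3%). The stated 12.8 is not reproduced; the gap is 14.3 − 12.8 = 1.5 points.

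**Step 2. Try other intervals at 24/30 = 80%.** For asymmetric intervals the half-width is half the total width.

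| Method | 95% interval (%) | Half-width (points) |
|---|---|---|
| Wald | 65.7 to 94.3 | 14.3 |
| Wilson | 62.7 to 90.5 | 13.9 |
| Jeffreys | 63.3 to 91.2 | 13.9 |
| Agresti-Coull | 62.3 to 90.9 | 14.3 |
| Clopper-Pearson | 61.4 to 92.3 | 15.4 |

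Further variants: arcsine 14.0, mid-p 14.3, logit 14.3, Wald with n − 1 in the denominator 14.6, Wald with a t quantile 14.9, Wald with continuity correction 16.0. All the two-sided 95% results lie between 13.9 and 16.0. A one-sided quantile (1.645) gives 12.0. None gives 12.8.

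**Step 3. Solve backwards from 12.8 with the Wald formula.**

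- Rate, keeping n = 30 and 95%: p = 0.849. At p = 0.85, 1.96 × √(0.85 × 0.15 / 30) = 0.1278, which rounds to 12.8.
- Sample size, keeping 80% and 95%: 1.96² × 0.16 / 0.128² = 37.5, so 38 subjects.
- Confidence level, keeping 80% and n = 30: z = 0.128 / √(0.16/30) = 1.753, which is 92.0%.

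The 85% match is the simplest explanation but not the only one: Agresti-Coull at 26/30 (86.7%) also has a half-width of 12.8. Either way the rate is not 80%.

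**Step 4. Precision for the endpoint as analysed.** For a mean of subject percentages, half-width = t(0.975, 29 df) × SD/√30 = 2.045 × SD/√30. The documents give no between-subject SD, so the SDs below are assumptions.

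| Assumed SD (points) | Half-width (points) |
|---|---|
| 15 | 5.6 |
| 20 | 7.5 |
| 30 | 11.2 |
| 40 | 14.9 |

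The break-even SD for ±12.8 is 12.8 × √30 / 2.045 = 34.3 points. The largest possible population SD when the mean is 80% is 100 × √(0.8 × 0.2) = 40 points, reached only if every subject completes all or none of the assessments.

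**Step 5. Check the companion statement.** For r = 0.5, n = 30 and a two-sided 5% level, the Fisher z approximation gives 81.4% power. That claim reproduces; the fault is confined to the compliance figure.

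**The case against.** The protocol names no formula and does not call the outcome binomial. Protocol 6.2 says the sample size rests on compliance seen in the sponsor's earlier research, which is not available here. A mean of subject percentages would give ±12.8 at an SD of about 34 points (t quantile) or 36 points (normal quantile), which is possible. On that view the figure is incompletely documented, not wrong. This does not rescue it. Sections 2.0 and 13.3 offer a rate and a sample size only, which a reader will take as binomial, and nothing in the documents supports so large an SD. What stands is that the source of the 12.8 is unknown and that 85% is an inference.

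The second objection is that little turns on the number. Thirty subjects are also justified by usual practice, the co-primaries are to be described without inferential tests, and no success threshold for compliance is visible. For the endpoint as analysed, ±12.8 is conservative unless the SD exceeds 34.3 points. All of this stands and limits the weight of the point. It is not a reason to leave an incorrect figure in two places.

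The third objection is to adding a CI to the SAP. Leaving one out is consistent with a descriptive plan, and parts of the SAP text are not visible. A CI also presupposes a settled estimator. SAP 3.1 counts days with data and SAP 3.2 counts sessions, and the dummy Table 2.1 carries both a mean (94.16) and an overall rate (92.95). This too stands: the addition is optional and should follow that choice.

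**Conclusion.** The concern holds. Under any standard two-sided 95% interval for a proportion, 80% in 30 subjects gives a half-width of at least 13.9 points; by Wald it is 14.3, against 12.8 stated. Either the rate or the half-width needs correcting, and the documents do not show which. This rests on reading the statement as binomial, the only reading its printed inputs support. For the mean of subject percentages, the half-width would be 5.6 to 14.9 points over assumed SDs of 15 to 40, so the printed figure cannot be called optimistic or pessimistic for the planned analysis. The point should be corrected, but the choice of 30 subjects does not depend on it.

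**What to change.** In Protocol 2.0 and 13.3, do one of the following:

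- restate the precision as ±14.3% at a compliance rate of 80%; or
- if the sponsor confirms that 85% was the planning rate, change the rate to 85% and keep ±12.8%.

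In both places name the formula (Wald, normal approximation) and add: *This treats each subject as one yes/no outcome; precision for the mean of subject-level percentages depends on the between-subject SD.*

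Optionally, once the sponsor has settled whether compliance counts days or sessions, add to SAP 3.2: *Overall compliance will be reported separately for n-back and for mood as the mean of subject-level percentages with a 95% CI from the between-subject SD (t distribution, number of subjects minus 1 df).*

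The cost is one corrected number and a short clarification in two protocol sections, plus one optional SAP sentence. Sample size, design and data collection stay as they are, and the interval uses the N, mean and SD already planned in SAP 6.6.
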